 - Any organism, virus, or infectious particle (e.g., prion protein transmitting transmissible spongiform encephalopathy), pathogenic or non-pathogenic, is considered an infectious agent. A transmission of an infectious agent may be suspected from clinical symptoms or laboratory findings that indicate an infection in a patient exposed to a medicinal product. This term applies only when contamination of the study drug is suspected.

Investigator Communications with Genentech:

Investigators must report all SAEs to Genentech within the timelines described below. The completed MDACC SAE reporting form/case report should be faxed immediately upon completion to Genentech Drug Safety at:

[name]

OR

[name]

Relevant follow-up information should be submitted to Genentech Drug Safety as soon as it becomes available.

Serious AE reports that are related to obinutuzumab and AEs of Special Interest (regardless of causality) will be transmitted to Genentech within fifteen (15) calendar days of the Awareness Date.

Serious AE reports that are unrelated to obinutuzumab will be transmitted to Genentech within thirty (30) calendar days of the Awareness Date.

Additional reporting requirements to Genentech include the following:

Any reports of pregnancy following the start of administration with the obinutuzumab and within the follow-up period (for female patients within one year after the last dose of obinutuzumab or the partner of a male patient within three months of completing therapy) will be transmitted to Genentech within 30 days of the Awareness Date.

All non-serious *obinutuzumab* AEs originating from the study will be forwarded Genentech *quarterly*

Note: Investigators should also report events to their IRB as required.

Follow-Up Information

Additional information may be added to a previously submitted report by any of the following methods:

Adding to the original **MDACC** SAE report and submitting it as follow-up

Adding supplemental summary information and submitting it as follow-up with the original MDACC SAE reporting form. Summarizing new information and faxing it with a cover letter including patient identifiers (i.e., D.O.B. initial, patient number), protocol description and number, if assigned, brief AE description, and notation that additional or follow-up information is being submitted (The patient identifiers are important so that the new information is added to the correct initial report). Occasionally Genentech may contact the reporter for additional information, clarification, or current status of the patient for whom and AE was reported. For questions regarding SAE reporting, you may contact the Genentech Drug Safety representative noted above or the MSL assigned to the study. Relevant follow-up information should be submitted to Genentech Drug Safety as soon as it becomes available and/or upon request.

Investigator Communications with Celgene:

Pregnancies

Pregnancies and suspected pregnancies (including a positive pregnancy test regardless of age or disease state) of a female subject occurring while the subject is on lenalidomide, or within 28 days of the subject's last dose of lenalidomide, are considered immediately reportable events. Lenalidomide is to be discontinued immediately. The pregnancy, suspected pregnancy, or positive pregnancy test must be reported to Celgene Drug Safety immediately by facsimile or email using the Pregnancy Initial Report Form. The female subject should be referred to an obstetrician-gynecologist, preferably one experienced in reproductive toxicity for further evaluation and counseling.

The Investigator will follow the female subject until completion of the pregnancy, and must notify Celgene Drug Safety immediately about the outcome of the pregnancy (either normal or abnormal outcome) using the Pregnancy Follow-up Report Form. If the outcome of the pregnancy was abnormal (e.g., spontaneous or therapeutic abortion), the Investigator should report the abnormal outcome as an AE. If the abnormal outcome meets any of the serious criteria, it must be reported as an SAE to Celgene Drug Safety immediately by facsimile, or other appropriate method, within 24 hours of the Investigator's knowledge of the event using the SAE Report Form.

All neonatal deaths that occur within 28 days of birth should be reported, without regard to causality, as SAEs. In addition, any infant death after 28 days that the Investigator suspects is related to the in utero exposure to the IP should also be reported to Celgene Drug Safety immediately by facsimile, or other appropriate method, within 24 hours of the Investigator's knowledge of the event using the SAE Report Form.

Male Subjects

If a female partner of a male subject taking investigational product becomes pregnant, the male subject taking lenalidomide should notify the Investigator, and the pregnant female partner should be advised to call their healthcare provider immediately.

Celgene Drug Safety Contact Information:
Celgene Corporation
Global Drug Safety and Risk Management
[name]
[name]
[name]
[contact]
E-mail: [contact]

Expedited Reporting by Investigator to Celgene

For the purpose of regulatory reporting, Celgene Drug Safety will determine the expectedness of events of being related to lenalidomide based on the Investigator Brochure. In the United States, all suspected unexpected serious adverse reactions (SUSARs) will be reported in an expedited manner in accordance with 21 CFR 312.32.

Serious adverse events (SAE) are defined above. The investigator must inform Celgene in writing using the MDACC SAE reporting form of any SAE within 24 hours of being aware of the event. The written report must be completed and supplied to Celgene by facsimile within 24 hours/1 business day. The initial report must be as complete as possible, including an assessment of the causal relationship between the event and the investigational product(s). Information not available at the time of the initial report (e.g., an end date for the adverse event or laboratory values received after the report) must be documented on a follow-up report. A final report to document resolution of the SAE is required. The Celgene tracking number (RV-CL-CLL- PI-004319) and the institutional protocol number should be included on SAE reports (or on the fax cover letter) sent to Celgene. A copy of the fax transmission confirmation of the SAE report to Celgene should be attached to the SAE and retained with the patient records.

REFERENCES

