Tumor Lysis Syndrome

For patients with evidence of TLS, obinutuzumab should be discontinued and the patient treated as clinically indicated. Following the complete resolution of TLS complications, obinutuzumab may be re administered at the full dose during the next infusion in conjunction with prophylactic therapy.

Lenalidomide

Lenalidomide will be provided to research subjects for the duration of their participation in this trial at no charge to them or their insurance providers and in accordance with the Revlimid REMS® program of Celgene Corporation. Per standard Revlimid REMS ® requirements all physicians who prescribe lenalidomide for research subjects enrolled into this trial, and all research subjects enrolled into this trial, must be registered in and must be filled within 14 days, unless the patient is a female of childbearing potential, in which case the prescription must be filled within 7 days. Only enough lenalidomide for one cycle will be supplied to the patient each cycle.

Lenalidomide will be given at 5 mg per day, day 9-56, followed by 10 mg per day, day 57 until end of treatment. Lenalidomide will start on day 9 and continued for one year with the possibility to prolong the end of treatment until progression or excessive toxicity. Patients will self administer lenalidomide daily, per mouth.

Dosage modification and Toxicity management of lenalidomide

If a dose of lenalidomide is missed, it should be taken as soon as possible on the same day. If it is missed for the entire day, it should not be made up.

Patients who take more than the prescribed dose of lenalidomide should be instructed to seek emergency medical care if needed and contact study staff immediately.

The dose of lenalidomide will be adapted depending on the assessment of toxicity. The evaluation of potential treatment-induced toxicity, in particular of hematological toxicity, in patients with advanced CLL/PLL required careful consideration. At diagnosis, in fact, cytopenia could be the expression of progressive bone marrow failure. As a consequence, dose modification decisions for patients with cytopenia (below the lower limit of the normal range) at baseline will be based on the NCI grading scale for haematological toxicity in CLL/PLL studies (see Table 2). For patients with a normal neutrophils count, platelet count and or hemoglobin value at baseline, the NCI common terminology criteria for adverse events (CTCAE) version 4.0 will be used (Appendix 3).

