We will monitor futility and safety of the treatment combination using a Bayesian design by Thall, Simon and Estey, in cohort size of 10. Specifically, assuming a beta (0.8, 1.2) prior for the overall response (OR) rate, we will stop trial if $\text{Prob}\{p(\text{OR}) > 0.40 \text{ data}\} < 0.05$, where $p(\text{OR})$ is the probability of overall response. That is, if at any time during the trial we determine that there is less than 5% chance that the overall response rate is at least 40%, we will stop the trial. For futility monitoring purpose, we will assess patients' OR rate at 3 months post treatment, and at each planned cohort (i.e., 10, 20, 30, etc.) for interim look, if there is not enough number of responders (such as 1 or fewer out of the first 10, 4 or fewer out of the first 20, etc.) we will temporarily suspend accrual until all patients in the current cohort has been fully evaluated. Similarly, we will stop the trial if $\text{Prob}\{p(\text{TOX}) > 0.50 \text{ data}\} > 0.95$, where $p(\text{TOX})$ is the probability of grade 3 or higher non-hematological toxicity and a beta(1, 1) prior was used for toxicity rate. That is, if at any time during the trial we determine that there is more than 95% chance that the toxicity rate is at least 50%, we will stop the trial due to safety concern. The corresponding stopping boundaries for futility and safety are shown in Tables 7 and 8 respectively. The operating characteristics of the design are illustrated in Table 9. Multc Lean Desktop (v2.1.0) was used for generating the stopping boundaries and the OC table.

If the trial did not stop due to either futility or toxicity, then with a total sample size of 30, the 95% credible interval for the overall response rate will be (0.24, 0.57), assuming an OR rate of 0.40 and a beta(0.8, 1.2) prior.

The proportion of patients achieving OR and its 95% credible interval will be presented. In addition, we will compute the posterior probability of OR rate being greater than 40%. Similar methods will be used to analyze the toxicity data. Univariate and multivariable logistic regression models will be fit to assess the association between OR and prognostic biomarkers. The time-to-event outcomes (such as time to next treatment or overall survival) will be estimated using the Kaplan-Meier method.

Table 7. Interim futility stopping boundaries in cohort size of 10.

Number of Patients Evaluated	Stop the trial if \leq OR Observed
10	1
20	4
30	7

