Table 8. Interim toxicity stopping boundaries in cohort size of 10.

Among These Number of Patients	Stop the trial if >/= Toxicity Observed
10	8
20	14
30	20
-	-

Table 9 The operating characteristics of futility and toxicity monitoring.

True OR rate	True Toxicity Rate	Prob (stop early)	Average number of patients
0.3	0.3	0.28	25.6
0.3	0.5	0.35	24.5
0.3	0.7	0.75	17.8
0.4	0.3	0.08	28.7
0.4	0.5	0.16	27.4
0.4	0.7	0.68	19.1
0.5	0.3	0.02	29.7
0.5	0.5	0.10	28.3
0.5	0.7	0.65	19.6

In addition, we will monitor the grade 4 and grade 5 non-hematological toxicities separately, throughout the study and in cohort size of 10. Specifically, the trial will be stopped if $\text{Prob}\{p(\text{TOX4}) > 0.25 | \text{data}\} > 0.95$ or $\text{Prob}\{p(\text{TOX5}) > 0.10 | \text{data}\} > 0.95$, where $p(\text{TOX4})$ and $p(\text{TOX5})$ are the probabilities of grade 4 and grade 5 non-hematological toxicities, respectively. A beta(0.5, 1.5) prior is assumed for $p(\text{TOX4})$ and a beta(0.2, 1.8) prior is assumed $p(\text{TOX5})$. Based on these stopping criteria, the trial will be stopped early if $[\#\text{patients with grade 4 toxicities}] / [\#\text{patients evaluated}] \geq 6/10, 9/20, 12/30$ OR $[\#\text{patients with grade 5 toxicities}] / [\#\text{patients evaluated}] \geq 4/10, 5/20, 7/30$.

This protocol will use PDMS and CORE as database repositories

REPORTING OF ADVERSE EVENTS ASSESSMENT OF SAFETY

Safety assessments will consist of monitoring and reporting AEs and SAEs that are considered related to obinutuzumab or/and lenalidomide, all events of death, and any study specific issue of concern.

Adverse Events

An AE is any unfavorable and unintended sign, temporarily associated with the use of an

investigational medicinal product (IMP) or other protocol- imposed intervention , regardless of attribution.

Serious Adverse Event Reporting for MD Anderson- Sponsored IND Protocols

An adverse event or suspected adverse reaction is considered “serious” if, in the view of either the investigator or the sponsor, it results in any of the following outcomes:

Death

A life-threatening adverse drug experience – any adverse experience that places the patient, in the view of the initial reporter, at immediate risk of death from the adverse experience as it occurred. It does not include an adverse experience that, had it occurred in a more severe form, might have caused death.

Inpatient hospitalization or prolongation of existing hospitalization

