It results in a congenital anomaly/birth defect in a neonate/infant born to a mother exposed to the IMP. It is considered a significant medical event by the investigator based on medical judgment (e.g., may jeopardize the patient or may require medical/surgical intervention to prevent one of the outcomes listed above).

METHODS AND TIMING FOR ASSESSING AND RECORDING SAFETY VARIABLES

The investigator is responsible for ensuring that all AEs and SAEs, that are observed or reported during the study, are collected and reported to the U.S. Food and Drug Administration (FDA), appropriate IRB(s), and Genentech, Inc. in accordance with CFR 312.32 (IND Safety Reports).

Adverse Event Reporting Period

The study period during which all AEs and SAEs must be reported begins after informed consent is obtained and initiation of study treatment and ends 30 days following the last administration of study treatment or study discontinuation/termination, whichever is earlier. After this period, investigators should only report SAEs that are attributed to prior study treatment.

Assessment of Adverse Events

All AEs and SAEs whether volunteered by the patient, discovered by study personnel during questioning, or detected through physical examination, laboratory test, or other means will be reported appropriately. Each reported AE or SAE will be described by its duration (i.e., start and end dates), regulatory seriousness criteria if applicable, suspected relationship to the obinutuzumab (see following guidance), and actions taken.

To ensure consistency of AE and SAE causality assessments, investigators should apply the following general guideline:

Yes

There is a plausible temporal relationship between the onset of the AE and administration of the obinutuzumab and the AE cannot be readily explained by the patient's clinical state, intercurrent illness, or concomitant therapies; and/or the AE follows a known pattern of response to the obinutuzumab and/or the AE abates or resolves upon discontinuation of the obinutuzumab or dose reduction and, if applicable, reappears upon re-challenge.

No

Evidence exists that the AE has an etiology other than the obinutuzumab (e.g., preexisting medical condition, underlying disease, intercurrent illness, or concomitant medication); and/or the AE has no plausible temporal relationship to obinutuzumab administration (e.g., cancer diagnosed 2 days after first dose of obinutuzumab).

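### Do the toxicity stopping rules need a stated per-patient observation period before Table 9 can be relied on?

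*Combined protocol and SAP*

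**What the plan says.** All the relevant text on the rules is in Section 10, Method of Analysis, and the tables after it.

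- **Response.** For futility the plan uses the "OR rate at 3 months post treatment". At each cohort of 10, "if there is not enough number of responders", then "we will temporarily suspend accrual until all patients in the current cohort has been fully evaluated".
- **Grade 3+ toxicity.** p(TOX) "is the probability of grade 3 or higher non-hematological toxicity", with a beta(1, 1) prior. The trial stops "if at any time during the trial we determine that there is more than 95% chance that the toxicity rate is at least 50" per cent. Table 8 gives the boundaries 8/10, 14/20 and 20/30.
- **Grade 4 and 5 toxicity.** The plan states that "we will monitor the grade 4 and grade 5 non-hematological toxicities separately, throughout the study and in cohort size of 10". The boundaries are 6/10, 9/20, 12/30 and 4/10, 5/20, 7/30, with patients evaluated as the denominator.
- **Adverse event capture.** The reporting period "ends 30 days following the last administration of study treatment or study discontinuation/termination, whichever is earlier". It is not tied to the stopping rules.
- **Exposure.** Section 6 says lenalidomide is "continued for one year with the possibility to prolong the end of treatment until progression or excessive toxicity", so exposure runs well past month 3.

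**The concern.** Response has a time point and a follow-up condition; toxicity has neither. The phrases about any time and throughout the study say when a rule is applied. They do not say which part of a patient's follow-up counts. The only accrual hold is triggered by few responders, so it protects against toxicity only incidentally.

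Table 9 needs a complete yes/no toxicity status for all 10 or 20 patients at each look. Suppose the count were read once, when patients 10 and 20 enrol, with no hold. At a 3-month toxicity rate of 0.70 the grade 3+ rule would then stop with probability 0.12-0.31 at 3 patients per month and under 0.01 at 6 per month, against 0.65 with full follow-up. On the same reading at 3 per month, the grade 4 rule at a true rate of 0.50 would stop with probability 0.36-0.68 against 0.76, and the grade 5 rule at 0.20 with 0.17-0.38 against 0.38. These are the trial's formal safety rules, so a loss of that size would matter. The ranges reflect assumed later hazards of 0 to 100% of the hazard in the first 3 months.

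**Working it through.** **1. Reproduce the plan's figures.** Inputs are the priors, cut-offs and cohort size in Section 10. With t events in n patients, the posterior for grade 3+ toxicity is beta(1+t, 1+n−t). Pr(rate > 0.50) is 0.887 at 7/10, 0.967 at 8/10, 0.905 at 13/20 and 0.961 at 14/20. The boundaries 8 and 14 are therefore right. The grade 4, grade 5 and futility boundaries also reproduce.

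For the Table 9 row with OR 0.4 and toxicity 0.7, assume independent outcomes, complete status and looks at 10 and 20:

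- Toxicity stops at 10 with probability 0.383 and at 20 with 0.266, in total 0.649. Passing: 0.617 at the first look, 0.351 at both.
- Futility stops at 10 with probability 0.046 and by 20 with 0.078. Passing: 0.954 and 0.922.
- Prob(stop early) = 1 − 0.351 × 0.922 = 0.68 (Table 9: 0.68).
- Average N = 10 + 10 × 0.617 × 0.954 + 10 × 0.351 × 0.922 = 19.1 (Table 9: 19.1).

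The other eight rows agree to within 0.006 on probability and 0.1 on average N.

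**2. Does follow-up finish in time?** Under the plan's wording a cohort's count stays live until the next cohort is full. A count of events cannot fall, so a boundary that complete data would reach is reached at some point; only the date is uncertain. With even entry at r patients per month, patient k enters at (k−1)/r.

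- Patient 10 completes 3 months at 9/r + 3; patient 20 enters at 19/r.
- Patient 20 completes 3 months at 19/r + 3; patient 30 enters at 29/r.

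In both pairs the first time is no later than the second when 10/r ≥ 3, that is r ≤ 3.33 per month.

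| Rate per month | Cohort of 10 complete | Patient 20 enters | Cohort of 20 complete | Patient 30 enters |
|---|---|---|---|---|
| 1.5 | 9.0 | 12.7 | 15.7 | 19.3 |
| 3 | 6.0 | 6.3 | 9.3 | 9.7 |
| 6 | 4.5 | 3.2 | 6.2 | 4.8 |

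Across the 1-3 per month of Section 3, even with no accrual hold, the toxicity rule stops with the full-follow-up probability of 0.649. The same timing applies to the grade 4 and grade 5 rules.

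**3. Add the plan's own hold.** At 3 per month only one patient has reached month 3 when patient 10 enters. Responders cannot exceed 1, so the hold always applies there. At 6 per month none has reached month 3, so it applies again. I simulated even entry, a 3-month toxicity rate of 0.70 at constant hazard with none later, this hold, and reading as events accrue. Stopping for toxicity before the last entry is about 0.65 at 1-3 per month and 0.54-0.61 at 6 per month.

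Average N at 1-3 per month is about 19.5 at OR 0.40, against 19.1 in Table 9. At OR 0.66 (the response rate quoted in Section 1 for lenalidomide plus rituximab) it is 20.0-20.4. Full follow-up there gives 10 + 6.17 + 3.51 = 19.7, because futility almost never stops. The cost is 0.3-0.7 of a patient.

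**4. Is 6 per month realistic?** Section 5 gives 3-6 per month, yet both Sections 3 and 5 give 10-20 months for 30 patients. That implies 30/20 = 1.5 to 30/10 = 3 per month; at 6 per month accrual would take 5 months.

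**The case for a change.** The best opposing argument is that the hold works the wrong way round: an effective but toxic regimen is the least likely to trigger it. At 1.5 per month and OR 0.66 it applies with probability 0.05 at patient 10 and 0.002 at patient 20. That is true, but at that pace each cohort finishes 3 months well before the next one fills, so the hold is not needed. Where accrual is fast enough for it to matter, it is certain to apply at patient 10.

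A second argument is that, with the hold, stopping at 3 per month is only 0.12-0.55 if toxicity is not re-read when the hold ends. That would require staff to finish a three-month suspension and ignore toxicity, contrary to the at-any-time wording.

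A third is that counting every event to date departs from Table 9 in the other direction. At a 3-month rate of 0.30 with unchanged later hazard, stopping rises from 0.2% to 7% at 3 per month and 37% at 1.5 per month. The arithmetic stands. But in the 1.5 per month case the twenty patients have 3 + j/1.5 months of exposure (j = 0 to 19). Their mean cumulative toxicity is 1 − 0.7 × mean(0.7^(j/4.5)) = 1 − 0.7 × 0.522 = 0.63, above the 0.50 limit. Stopping then is what the rule is for. With a later hazard of 25% the figure is 0.5-1.4%.

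What stands is modest. Evaluated is not defined for toxicity, and patients who leave early without an event are not mentioned. If 10% did so (assumed) and the rest had rate 0.70, stopping would be 0.40, 0.75 or 0.65 according to whether they count as non-events, count as events or are replaced. Capture for 30 days after the last dose limits how many such patients there would be.

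**Conclusion.** No change to the plan is called for. The observation period is indeed unstated, but reading the rules as written roughly delivers Table 9: toxicity stopping of about 0.65 at a rate of 0.70, and less than one extra patient on average at 1-3 per month. The large losses come from a single count at enrolment, which the plan does not prescribe. Analysts would count each treated patient's events as they occur and act when a boundary is crossed.

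Fixing a 3-month window would match Table 9's label, but it would take later grade 3 events out of a rule that now runs throughout while lenalidomide continues. That is a trade-off, not a clear gain.

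The conclusion assumes even entry, most toxicity within 3 months, and accrual of no more than about 3.3 per month. Nearer 6 per month stopping would fall to 0.54-0.61. The accrual rates in Sections 3 and 5 disagree; that is a separate clerical matter and does not alter this conclusion.

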3. STUDY DESIGN DESCRIPTION OF THE STUDY

This is a single arm phase II study of Combination of Lenalidomide and Obinutuzumab in Patients with Chronic Lymphocytic Leukemia/Small Lymphocytic Lymphoma (CLL-SLL) with recurrent disease. Up to 30patients will be enrolled from M. D. Anderson Cancer Center, at a rate of 1-3patients per month. The primary efficacy endpoint is overall response and safety is one of the secondary endpoints. We will monitor futility and safety of the treatment combination using a Bayesian design by Thall, Simon and Estey, in cohort size of 10.

Response to treatment will be assessed according to NCI-WG 2008 working group criteria at 3, 6 months from the beginning of therapy and every 6 months thereafter. The investigator assessment of response and progression will be considered primary for all endpoints described in the study.

The estimated patient accrual is 1-3 per month. And the trial accrual time is estimated to be about 10-20 months. The end of study is defined as 5 years after the last patient was enrolled (unless all patients have died).

OUTCOME MEASURES

Efficacy Outcome Measures

Response will be assessed by means of clinic visits, complete blood counts, imaging if clinically indicated radiographic images as clinically indicated).

Clinic visits (this will include vital signs and physical exam) at the University of Texas, M D Anderson Cancer Center (UTMDACC) are required after 3, 6 cycles (obinutuzumab and lenalidomide) and 12 cycles (lenalidomide) and once every 6 cycles thereafter. Hematology complete blood counts (white blood cells, hemoglobin, platelets and differential) will be monitored once weekly for the first five weeks and once every two weeks in case of dose increase until a stable, dose of lenalidomide has been established for the specific patient. Blood will be drawn for routine tests.

Bone marrow biopsy and aspiration will be performed and evaluated by flow cytometry after 3, 6 cycles (obinutuzumab and lenalidomide) and after 12 cycles (lenalidomide). If patients stay on the study past 12 cycles, once every 6 cycles, they will have if clinically indicated a bone

marrow biopsy and aspirate evaluated by flow cytometry to check the status of the disease .

Safety Outcome Measures

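### Does Table 9 misstate the chance of early stopping because it leaves out the grade 4 and grade 5 rules?

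*Combined protocol and SAP*

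**What the plan says.** Section 10, Method of Analysis, gives two rules first. The trial stops for futility if the posterior probability that the response rate exceeds 0.40 falls below 0.05, with a beta(0.8, 1.2) prior. It stops for safety if the posterior probability that the rate of grade 3 or higher non-hematological toxicity exceeds 0.50 is above 0.95, with a beta(1, 1) prior. Tables 7 and 8 give the boundaries. Then comes the sentence "The operating characteristics of the design are illustrated in Table 9". The table is captioned "Table 9 The operating characteristics of futility and toxicity monitoring", and its scenarios vary one response rate and one toxicity rate.

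Below the table a new paragraph begins "In addition, we will monitor the grade 4 and grade 5 non-hematological toxicities separately". It sets limits of 0.25 for grade 4 and 0.10 for grade 5, each with its own prior. It continues "Based on these stopping criteria, the trial will be stopped early if" and lists counts of 6/10, 9/20, 12/30 for grade 4 and 4/10, 5/20, 7/30 for grade 5.

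On timing, Section 3 describes monitoring "using a Bayesian design by Thall, Simon and Estey, in cohort size of 10", and Section 10 places the futility assessment "at each planned cohort (i.e., 10, 20, 30, etc.) for interim look". The explanation of the futility criterion nevertheless reads "if at any time during the trial we determine that there is less than 5% chance", and the toxicity criterion is explained with the same opening words.

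**The concern.** The trial has four binding stopping rules, and the text presents Table 9 as describing the design. If the table reflects only two of them, a reader who takes its stopping probability as the chance that this trial ends early gets too low a figure, and too high an expected sample size. The caption does not fully settle the matter, since grade 4 and grade 5 events are toxicity too.

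The timing phrase raises a smaller doubt. Continuous monitoring and looks every 10 patients can give different decisions on the same data, and Table 9 would fit only the second.

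**Working it through.** **Inputs.** Priors, thresholds and boundaries come from Section 10 and Tables 7 and 8. The maximum is 30 patients in cohorts of 10. A stop at 30 is not early, so only the looks at 10 and 20 count. Response and toxicity are taken as independent.

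**Boundaries.** Recomputing the beta posteriors gives all 12 printed boundaries. At 20 patients, for example:

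| Rule | At the boundary | One event short of stopping |
|---|---|---|
| Futility (stop if below 0.05) | 4 responses: 0.030 | 5 responses: 0.081 |
| Grade 3 or higher (stop if above 0.95) | 14 events: 0.961 | 13 events: 0.905 |
| Grade 4 | 9 events: 0.965 | 8 events: 0.913 |
| Grade 5 | 5 events: 0.959 | 4 events: 0.875 |

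**Table 9 with two rules.** Let R(n) and T(n) be the probabilities of passing the response and toxicity rules at every look up to n. Then

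- Prob(stop early) = 1 − R(20) × T(20)
- average N = 10 + 10 × R(10) × T(10) + 10 × R(20) × T(20)

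Row with response 0.4 and toxicity 0.5:

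- R(10) = 1 − 0.6^10 − 10 × 0.4 × 0.6^9 = 1 − 0.0060 − 0.0403 = 0.9536
- T(10) = 1 − (45 + 10 + 1)/1024 = 0.9453
- carrying the surviving counts to the second look: R(20) = 0.9219, T(20) = 0.9111
- Prob(stop early) = 1 − 0.9219 × 0.9111 = 0.160; printed 0.16
- average N = 10 + 9.015 + 8.400 = 27.41; printed 27.4

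The nine rows in table order come out at 0.285/25.64, 0.348/24.56, 0.749/17.76, 0.080/28.72, 0.160/27.41, 0.677/19.12, 0.016/29.71, 0.102/28.33 and 0.654/19.56. All agree with print within 0.006 in probability and 0.07 patients. Table 9 is therefore the two-rule calculation, and it is correct.

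**All four rules.** The documents give no true grade 4 or grade 5 rates, so these are assumptions. Each patient is counted once by worst grade, and grade 3 takes the remainder of the toxicity rate. In the same row with grade 4 = 0.25 and grade 5 = 0.10 (grade 3 = 0.15), T(10) falls to 0.9254 and T(20) to 0.8476:

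- Prob(stop early) = 1 − 0.9219 × 0.8476 = 0.219
- average N = 10 + 10 × 0.9536 × 0.9254 + 10 × 0.9219 × 0.8476 = 26.64

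Largest rise over the two-rule probability in any row that can hold the assumed rates:

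| Assumed grade 4 / grade 5 | Largest rise | Row (response / toxicity) |
|---|---|---|
| 0.05 / 0.02 | 0.0001 | 0.4/0.3 and 0.5/0.3 |
| 0.10 / 0.05 | 0.003 | 0.5/0.3 |
| 0.20 / 0.05 | 0.016 | 0.5/0.3 (0.016 to 0.032) |
| 0.20 / 0.10 | 0.059 | 0.5/0.3 (0.016 to 0.075) |
| 0.25 / 0.10 | 0.063 | 0.5/0.5 (0.102 to 0.165) |

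The rows with toxicity 0.3 cannot hold the last pair, because 0.25 + 0.10 = 0.35. In the rows with toxicity 0.7 the last pair adds at most 0.011. On its own and at its own limit, the grade 4 rule stops early with probability 0.050 and the grade 5 rule with probability 0.047.

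**Timing.** Six grade 3 or higher events in 7 patients give a posterior of 0.965, above the threshold. If the next three patients have none, 6 in 10 gives 0.726, short of the boundary of 8. The two readings can therefore differ, but boundaries are printed only for 10, 20 and 30, and Section 3 and Section 10 both name cohorts of 10.

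**The case for a change.** The best case for a change is that a stopping rule is part of the design wherever it stands in the text, and no sentence confines Table 9 to the first two. In relative terms the gap can be large: with response 0.5 and grades 3, 4 and 5 at 0.10 each, the printed 0.02 becomes 0.062. Beyond the limits it grows further: with response 0.4, toxicity 0.3 and grade 4 and grade 5 at 0.15 each, 0.080 becomes 0.245. A clarifying phrase would cost almost nothing.

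Part of this stands. Table 9 is not a four-rule summary and should not be cited as one. But when the text refers to the design, it has described exactly two rules and pointed to their two boundary tables. The caption names the same two kinds of monitoring, and a table with a single toxicity rate visibly cannot evaluate rules on grade 4 and grade 5 separately. The large gaps arise where fatal toxicity is at or above 10%, which the grade 5 rule exists to catch; they do not show that a sound treatment would be stopped more often than the plan implies. A re-run would also need grade splits that the plan does not supply, so it would describe the chosen assumptions as much as the design.

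**Conclusion.** No change is needed. It is true that Table 9 omits the grade 4 and grade 5 rules and so bounds the four-rule results from one side, apart from rounding. This is a matter of how widely one phrase is read, and the arithmetic is sound: the 12 boundaries and nine rows all reproduce.

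At assumed grade 4 and grade 5 rates up to 0.10 and 0.05 the difference is about 0.003 or less, under half a unit of the table's second decimal. It reaches about 0.06 only around the rules' own limits, where stopping is intended. These sizes rest on the assumed rates, on independence of response and toxicity, and on counting each patient once by worst grade. If fatal cases also counted toward the grade 4 rule, stopping would rise further and the direction of the bound would hold.

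The timing phrase explains the posterior criterion in words and does not set a schedule. The same paragraph, Section 3 and the boundary tables fix the looks at cohorts of 10, and an analyst would apply them that way.
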